#### 12.1.2 Blinding

All site staff at the investigative sites, Sponsor, CROs, and vendors as well as all enrolled subjects will be masked to the study drug assignments throughout the trial. One pre-designated statistician will have access to the blinded treatment assignments and be responsible for all activities that require unblinding, including the per protocol Interim Efficacy Analysis (Section 17.4).

#### 12.1.3 Unblinding

In the event of an emergency, the Investigator (or designee) should contact the Study Medical Monitor to discuss the case before unblinding of an individual subject's treatment code is broken by the site. If the medical condition of the subject warrants immediate unblinding, the treatment assignment of the subject may be obtained from the IRT without first consulting the Study Medical Monitor. However, the site must contact the Study Medical Monitor as soon as possible after the unblinding.

An interim efficacy analysis will be performed after approximately 50% of the enrolled subjects have completed their Day 56 Visit and their data have been recorded. The single pre-designated unblinded statistician described above in Section 12.1.2 will perform this analysis. The specifics of this interim analysis will be included in the Statistical Analysis Plan.

### 12.2 Subject Informed Consent

Written consent will be obtained from the subject prior to any study-specific procedure or investigation.

Information about the study, explaining the objectives and potential risks and benefits, will be given to the subject in writing and verbally in a language that is understood by the subject. The subject should have adequate time to read the information and to ask the Investigator any questions. The Investigator must be satisfied that the subject has understood the information provided before written consent is obtained.

If a subject agrees to participate, he/she will be asked to sign and date an informed consent form (ICF), the original copy of which will be kept by the Investigator. A copy of the signed ICF will be given to the subject.

### 12.3 Study Periods

The clinical trial will consist of the following periods:

- Screening: Days -21 through Day 1 Pre-dose
- Treatment: Day 1 Dosing through Day 28
- Observation: Day 29 through Day 84

### 12.4 Study Procedures per Period and Visit

❖ *Procedures that relate only to the PK Study Sub-Cohort will be denoted by a diamond similar to the one at the beginning of this paragraph.*

#### 12.4.1 Screening Period

The Screening Period begins immediately following the ICF signing (see Section 12.2 for a description of the informed consent procedures).

##### ✓ *Screening Visit (Day -21 to Day -1)*

The following procedures are to be performed during the Screening Visit:

- Site personnel confirm that the ICF: (a) is the most current ICF; (b) was signed and dated by the subject, (c) was witnessed; and (d) was copied with one copy given to the subject for their personal records
- Demographics recorded
- Medical history recorded
- Concomitant medications documented
- Adverse events that occur following ICF signing will be recorded
- Height and weight recorded

- Vital Signs: oral temperature, peripheral blood pressure, heart rate, and respiratory rate will be recorded
- Physical examination
- Clinical laboratory tests: Fasting status will be recorded
- Urine pregnancy test will be performed in all females and the results will be recorded
- 12-lead ECG tracing recorded as per the ERT manual. An original (duplicate) copy of the ECG is required for trial documentation. This ECG will also be transmitted to the central ECG laboratory.
- Scalp and face examination by PI (or designee) with selection of a Treatment Field that meets the criteria stated in Section 11.1. The Treatment Field Map and Template will be prepared as per the Investigator
- AK lesions count (11.1.5) and grading (11.1.1)
- Study Drug Measurement and Application review (see Section 13.6.3). Subject will be trained to measure (using placebo ointment on the Dosing Card) and to accurately apply the study drug, without actually applying placebo ointment to their Treatment Field
- Subject instructions review will be reviewed including appointment for the next visit
- Inclusion and exclusion (enrollment) criteria applied by Investigator and recorded
- Investigator may declare of subject's potential eligibility for PK Study Sub-Cohort

Subjects who are eligible for the **PK Study Sub-Cohort** will undergo the following additional safety assessments:

- ❖ Review additional Exclusion Criteria for PK subjects
- ❖ Toxicology and drug screen
- ❖ Alcohol level

**✓ Day 1 Pre-Dose Visit**

Subjects who have completed all screening procedures and continue to meet the study enrollment criteria will return to the investigative site on Day 1 Pre-Dose. During this visit, the following procedures will be performed:

- Vital signs: oral temperature, peripheral blood pressure, heart rate, and respiratory rate will be recorded
- Adverse event(s): volunteered, elicited, and observed AEs will be recorded

- Concomitant medications documented
- Study Drug Measurement and Application review (see Section 13.6.3) should be one of the first procedures performed upon arrival at the site. The Treatment Field Map and Template will be prepared as per the Investigator instruction sheet.
- Subject will be trained to measure (using placebo ointment on the Dosing Card) and to accurately apply the study drug, without actually applying placebo ointment to their Treatment Field
- Physical examination
- Fitzpatrick skin typing (Section 9.3.2)
- Local Skin Reaction Score (baseline)
- AK Lesions in the Treatment Field: baseline count (11.1.5) and grading (11.1.1)
- Urine pregnancy test will be performed in all females and results recorded.
- 12-lead ECG tracing will be recorded as per the ERT manual. An original (duplicate) copy of the ECG is required for trial documentation. This ECG will also be transmitted to the central ECG laboratory
- Study Drug Application: Training and Testing (see Section 13.6.3) should be repeated after all the above activities have been completed. Subject will be trained to measure (using placebo ointment on the Dosing Card) and to accurately apply the study drug, without actually applying placebo ointment to their Treatment Field.
- Safety data from Screening, all available data from the Day 1 Pre-Dose Visit, as well as the Enrollment Criteria will be reviewed and approved by the Investigator (or designee)

Subjects who meet the study enrollment criteria will undergo the following procedures:

- Randomization of subjects
- Clinical laboratory tests: Fasting status will be recorded.
- Photographs of Treatment Field at designated sites
- Study drug weighed and recorded

Subjects enrolled in the **PK Study Sub-Cohort** will undergo the following additional procedure:

- ❖ Notify IWRS that the subject was enrolled in the PK Study Sub-Cohort to enable proper randomization and treatment assignment
- ❖ Blood sampling for (baseline) PK

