
To qualify for the study, subjects aged 18 (inclusive) or older must have signed informed consent and met the study enrollment criteria that include having 4-8 discrete Grade 1 or 2 AK
	

lesions within a 25 cm^2 area on the scalp or face ("the Treatment Field"). Subjects will be randomly assigned in a double-blind fashion to 1 of 3 parallel treatment cohorts (5%, or 10% VDA-1102, or placebo, respectively) in a ratio of 1:1:1. Randomized subjects will apply a single thin application of the study drug to their Treatment Field for 28 days.

This clinical trial will include 3 study periods.

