#### 11.1.3 Treatment Field Selection

Any 25 cm^2 contiguous area on the face or scalp of the subject that contains 4-8 AK lesions that meet the requirements stated in AK Lesion Eligibility criteria (section 11.1.2) may be selected as the study Treatment Field. The Treatment Field will be selected at Screening and confirmed on Day 1 Pre-Dose. If the Treatment Field selected at Screening is no longer eligible at Day 1 Pre-Dose, a new Treatment Field may be selected on Day 1 Pre-Dose.

It is recommended that the Treatment Field be a square or rectangle and that is visible to the subject when looking in the mirror. Treatment Fields not visible to the subject when looking in the mirror are best managed by having a dosing partner help with the dosing. Dosing partners must accompany the subject on Day 1 so as to undergo training and testing like all the subjects who self-dose.

The Treatment Field or its outer border must **not** be:

- a) Within 2.5 cm (~1 inch) of either labial commissure of the mouth, lip vermillion border, palpebral fissure or a suspected or proven malignancy;
- b) Close to another active dermatologic process that could spread to the Treatment Field and interfere with the proper assessment of the Treatment Field and/or its included AK lesions; or
- c) So close to the eyebrows, beard, or other area with hair as to interfere with proper application of the study drug or assessment of the Treatment Field.

**NOTE: Ideally other AKs should NOT be adjacent to the border of the Treatment Field which could confound the AK lesion counting or identification of the Treatment Field at subsequent study visits.**

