## 17. STATISTICAL PLAN

### 17.1 Sample Size Rationale and Justification

The primary objective of the trial is to compare the reduction on Day 56 in the number of the AK lesions (or % reduction if baseline measure will be found different between the groups) in the Treatment Field of subjects receiving 5% or 10% VDA-1102 ointment to the reduction in the number of AK lesions in subjects receiving placebo. The sample size calculation was based on demonstrating an effect size of 0.83 using a two group t-test with a 0.045 two-sided significance level. The total significance level of 5% was divided between the interim analysis 0.5% (0.005) and the final analysis 4.5% (0.045). The sample size calculation was based on the final significance. The spending function calculation for alpha will be performed using the O'Brien-Fleming approach. Assuming a drop-out rate of 10%, approximately 84 subjects will be recruited in order to complete the study with a sample of approximately 75 evaluable subjects.

A sample size of 25 in each group will have 80% power to detect an effect size of 0.83 using a two group T-test with a 0.045 two-sided significance level.

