### 5.6.2 Derived Data

#### 5.6.2.1 Definition of baseline

5.6.2.1.1 Baseline is defined as the last non-missing value prior to the patient start of treatment (i.e., Day1 Pre-dose, if available, otherwise Screening). All tabulations involving change from baseline data will only include patients with data at baseline and at follow-up.

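### Two pre-dose AK counts are collected, but the SAP's ANCOVA and mixed model prespecify neither as a covariate: a modest loss of efficiency

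*Protocol*

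**What the plan says.** Protocol section 12.4.1 lists "AK lesions count (11.1.5) and grading (11.1.1") among the Screening Visit procedures (Day -21 to Day -1) and "AK Lesions in the Treatment Field: baseline count (11.1.5) and grading (11.1.1") among those of the Day 1 Pre-Dose Visit, before randomization. Protocol section 7.1 has the Screening field requalified on Day 1, so both counts normally refer to the same skin. Section 11.1.3 gives the exception: "If the Treatment Field selected at Screening is no longer eligible at Day 1 Pre-Dose, a new Treatment Field may be selected". Inclusion criterion 3 requires 4 to 8 qualifying lesions at both visits.

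The rule in SAP 5.6.2.1.1 is "Baseline is defined as the last non-missing value prior to the patient start of treatment (i.e., Day1 Pre-dose, if available, otherwise Screening").

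SAP 5.6.5.2 compares the Day 56 decrease between each active arm and placebo by t-test, rank-sum or median test, and also by ANCOVA. The ANCOVA adjusts for site and for suspected covariates that turn out to differ between arms. The mixed model in SAP 5.6.5.6 uses the same adjustment rule. Neither names a pre-dose count. Protocol section 17.2.1 does adjust its repeated-measures model for the baseline measure.

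On power, protocol section 17.1 states "A sample size of 25 in each group will have 80% power to detect an effect size of 0.83". The final test level given there is 0.045, two-sided.

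**The concern.** The change score at Day 56 contains the counting error of the Day 1 count in full. A second untreated count, taken 1 to 21 days earlier and usually on the same field, carries information about the same true starting value. As the SAP stands, Day 1 enters a model only if the arms happen to differ on it, and Screening has no planned role beyond the fallback.

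What is at stake is precision. With 25 evaluable subjects per arm and planned power just above 80%, even a few points from data already in the database are worth having.

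The fallback has a smaller problem. If a field was re-selected on Day 1 and its Day 1 count were missing, the Screening count would come from different skin.

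**Working it through.** **1. The plan's own figure.** Inputs from protocol section 17.1: effect size 0.83, 25 per group, two-sided 0.045. Noncentrality = 0.83 × √(25/2) = 2.934; df = 48; critical t = 2.058. Power is 80.7%, and 25 is the smallest group size that reaches 80%. With 10% dropout, 25/0.9 = 27.8, so 28 per arm and 84 in total. The stated figures reproduce.

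**2. Model.** Let T be the true count on Day 1, D the true change to Day 56, W the true drift from Screening to Day 1, and e the independent error of each count. Then Screening = T − W + e0, Day 1 = T + e1 and Day 56 = T + D + e2. The SDs are σT, σD, σw and σe. The documents give none of them, so all are assumptions.

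- Change from Day 1, unadjusted: variance = σD² + 2σe².
- ANCOVA with Day 1: residual variance = σD² + σe² + V1, where V1 = 1/(1/σT² + 1/σe²).
- ANCOVA with Day 1 and Screening: residual variance = σD² + σe² + V2, where V2 = 1/(1/σT² + 1/σe² + 1/(σe² + σw²)). V2 is below V1 whatever the drift.
- Screening without Day 1: the change is D + e2 − e1, which is uncorrelated with T − W + e0. Screening alone therefore explains almost nothing; the two counts work only together.
- Change from the mean of both counts: variance = σD² + 1.5σe² + σw²/4. Against the single baseline this alters the variance by −σe²/2 + σw²/4, so the gain is zero at σw² = 2σe² and becomes a loss beyond that.

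**3. Numbers.** Take σT = σD = 1.25, the middle of an assumed range of 1.0 to 1.5. Fix the effect at 0.83 SD of the change from Day 1. For σe = 1.0 and no drift:

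- Change variance = 1.5625 + 2 = 3.5625.
- V1 = 1/(0.64 + 1) = 0.610, so the residual is 3.172 and the effect is 0.83 × √(3.5625/3.172) = 0.880.
- V2 = 1/(0.64 + 1 + 1) = 0.379, so the residual is 2.941 and the effect is 0.83 × √(3.5625/2.941) = 0.914.

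Power uses the noncentral t, with one degree of freedom removed per covariate and site ignored:

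| σe | σw | t-test, Day 1 change | ANCOVA Day 1 | ANCOVA Day 1 + Screening | Gain from Screening | t-test, change from mean |
|---|---|---|---|---|---|---|
| 0.5 | 0 | 80.7% | 81.4% | 83.2% | +1.9 | 83.1% |
| 0.5 | 1.0 | 80.7% | 81.4% | 81.9% | +0.6 | 78.4% |
| 1.0 | 0 | 80.7% | 85.0% | 87.6% | +2.5 | 86.3% |
| 1.0 | 1.0 | 80.7% | 85.0% | 86.6% | +1.6 | 83.5% |

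**4. Check with counts.** The formulas ignore rounding and the 4–8 limit. Simulations with both pre-dose counts rounded and limited to 4–8 agree in direction. With a stable true count, σe of 0.5 to 1.25 and the other SDs at 1.0 to 1.5, adding Screening to Day 1 cut residual variance by 2–8% and raised power by 0.2 to 2.4 points. With drift included, the gain was about 0.1 to 3 points and never negative. Change from the mean gave 82–87% when drift SD was 0 or 0.5, but about 79–80% when drift SD was 1.0 and error SD 0.5.

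**The case against.** The strongest reply is that nothing here is wrong. The baseline rule is explicit, it agrees with the protocol's own label for the Day 1 count, and the last pre-dose value on the field actually dosed is a legitimate choice. That stands: there is no contradiction, no bias between arms and no error in the sample size.

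A reader might go further and infer that counting error could be averaged out at no cost by redefining baseline as the mean of the two counts. The documents do not support that, for four reasons:

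- Averaging halves the error variance of the baseline term and leaves the Day 56 error untouched.
- Stability between visits cannot be assumed. The gap can reach 21 days, restrictions on sun exposure and topical products begin at Screening, and the re-selection rule anticipates fields that no longer qualify.
- The Screening count helps to choose the field, so it is not a pure replicate.
- Half-lesion baselines would complicate the percentage-clearance analyses and the subgroup with at least one grade ≥2 lesion at baseline.

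It is also fair to say that much of the benefit comes from Day 1 alone, and that Screening then adds little. A separate simulation, putting the mean of the two counts into the ANCOVA in place of Day 1, found 1 point or less. What survives is that both counts precede randomization, so using them as covariates is valid and costs almost nothing.

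The fallback problem is nearly empty. A randomized subject needs a qualifying Day 1 count under inclusion criterion 3, so a re-selected field without one would already be an eligibility violation.

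**Conclusion.** The point holds as a modest, avoidable loss of efficiency. Two pre-dose counts exist for every subject, normally of the same field, and the SAP's adjusted models commit to neither. Adding Screening to a model that already contains Day 1 is worth about 0 to 3 power points. Entering both instead of relying on the unadjusted t-test is worth more: 80.7% against 81.9–87.6% in the four cases tabulated.

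These sizes rest on assumed error, drift and true-change SDs, and the documents allow none of them to be narrowed. The direction is firmer. Apart from the lost degree of freedom, a second covariate cannot raise the expected residual variance, whereas averaging can. The gain belongs to the ANCOVA and mixed model only; the unadjusted tests in SAP 5.6.5.2 are unaffected.

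This should not be read as showing that the trial is underpowered against its stated assumptions or that its treatment comparison is biased.

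**What to change.** Before unblinding, amend the SAP as follows:

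- **5.6.2.1.1:** keep Day 1 Pre-Dose as the AK-count baseline and change from Day 1 as the endpoint. Allow the Screening fallback only when the Treatment Field is unchanged.
- **5.6.5.2 and 5.6.5.6:** name the Day 1 count and the Screening count as fixed covariates, entered whether or not the arms differ on them. Where the field was re-selected on Day 1, use the Day 1 value in place of Screening.

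Do not require a baseline formed from the mean of the two counts.

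The cost is a few lines of SAP text, a derived Screening covariate with a flag for re-selected fields, and one degree of freedom for Screening beyond the one for Day 1. No visit, procedure or subject is added.

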## 12.4.2 Treatment Period

### ✓ **Day 1 Dosing Visit**

The following procedures will be performed on subjects selected to proceed to the Treatment Period.

- Study drug application and completion of the Dosing Diary by the subject under the supervision of the site personnel.
- Subject Instruction Packet will be reviewed including appointment for the next visit.
- Study drug and study tools will be given to the subject.

### ✓ **Day 1 Post-Dose through Day 6**

- Subjects will dose at home each evening, beginning with Day 1 and record the application in the Dosing Diary.

**Note: Subjects will receive 2 doses of the study drug on Day 1: once at the site after randomization and once in the evening at home.**

- Site personnel will communicate with the subjects once a week (Section 10.1.6) in order to review the Subject Instruction Packet and Dosing Diary as well as to remind each subject of their next site visit.

### ✓ **Day 7 Visit**

On Day 7 ( $\pm 2$ ) the following procedures will be performed:

- Adverse event(s) recorded
- Concomitant medications documented
- Study drug accountability and dosing compliance: study drug tubes will be weighed, the results recorded, and diaries reviewed and photocopied. Study drug and/or tools will be replenished, as needed.
- Vital signs: oral temperature, peripheral blood pressure, heart rate, and respiratory rate will be recorded.
- Local Skin Reaction Score in the Treatment Field
- AK Lesions in the Treatment Field: count (11.1.5) and grading (11.1.1)
- Study Drug Measurement and Application review (see Section 13.6.3)

- **The first 15 subjects randomized (Nested Phase 1b Safety Cohort) will undergo:**

- 12-lead ECG tracing will be recorded as per the ERT manual. An original (duplicate) copy of the ECG is required for trial documentation. This ECG will also be transmitted to the central ECG laboratory
- Clinical laboratory tests: fasting status will be recorded
- Physical examination

The following additional procedures will only be performed on the Day 7 Visit only in subjects enrolled in the subjects enrolled in the **PK Study Sub-Cohort**:

- ❖ PK blood sampling approximately 12 hours after the Day 6 dose

- Subject Instruction Packet will be reviewed including appointment for the next visit.
- Study drug and study tools will be given to the subject, as needed.

- ✓ ***Day 7 through Day 13***

- Subjects will dose at home each evening approximately 2 hours before bedtime and record the application in the dosing diary.
- Site personnel will communicate with the subjects once a week (Section 10.1.6) in order to review the Subject Instruction Packet and Dosing Diary as well as to remind each subject of their next site visit.

- ✓ ***Day 14 Visit***

On Day 14 ( $\pm 2$ ) the following procedures will be performed:

- Adverse event(s) will be recorded
- Concomitant medications documented
- Vital signs: peripheral blood pressure, respiratory and heart rates, and oral temperature will be recorded
- Physical examination
- Clinical laboratory tests: Fasting status should be recorded
- 12-lead ECG tracing will be recorded as per the ERT manual. An original (duplicate) copy of the ECG is required for trial documentation. This ECG will also be transmitted to the central ECG laboratory

- Local Skin Reaction Score in the Treatment Field
- AK Lesions in the Treatment Field: count (11.1.5) and grading (11.1.1)
- Study Drug Measurement and Application review (see Section 13.6.3)
- Study drug accountability and dosing compliance: study drug tubes will be weighed, the results recorded, and diaries reviewed and photocopied
- Study drug and study tools will be given to the subject, as needed

The following additional procedures will be performed on the Day 14 Visit only in subjects enrolled in the subjects enrolled in the PK Study Sub-Cohorts:

- ❖ PK blood sampling approximately 12 hours after the Day 13 dose
- Subject Instruction Packet will be reviewed including an appointment for the next visit will be given
- ✓ **Day 14 through Day 27**
  - Subjects will dose at home each evening approximately 2 hours before bedtime and record the application in the Dosing Diary.
  - Site personnel will communicate with the subjects once a week (Section 10.1.6) in order to review the Subject Instruction Packet and Dosing Diary as well as to remind each subject of their next site visit
- ✓ **Day 28 Visit**

On Day 28 ( $\pm 4$ ) the following procedures will be performed:

- Adverse event(s) AEs will be recorded
- Concomitant medications documented
- Vital signs: peripheral blood pressure, respiratory and heart rates, and oral temperature will be recorded
- Physical examination
- Local Skin Reaction Score in the Treatment Field
- AK Lesions in the Treatment Field: count (11.1.5) and grading (11.1.1)
- Study drug accountability and dosing compliance: study drug tubes will be weighed and the results recorded. Dosing Diaries will be collected and not returned

- 12-lead ECG tracing recorded as per the ERT manual. An original (duplicate) copy of each ECG is required. This ECG will also be transmitted to the central ECG laboratory
- Complete clinical laboratory tests: Fasting status to be recorded
- Urine pregnancy test will be performed at the investigative site in all females and the results will be recorded

The following Procedure will only be performed on the Day 28 Visit in subjects enrolled in the **PK Study Sub-Cohort**:

- ❖ PK blood sampling approximately 12 hours after the Day 27 dose. Additional blood samples will be collected at approximately 15, 18, and 21 hours post dose
- ❖ 24-hour ambulatory cardiac Holter monitor will be connected to the subject
- Trial instruction review including an appointment for the next visit will be given.

